The Effects of Preoperative Blood Flow Restriction Training in Patients Undergoing ACL Reconstruction

Protocol Version 2.0:
October 28, 2022

Principle Investigator:
[name]
Resident Physician, Division of Orthopaedic Surgery, University of Toronto

Primary Supervisor:
[name]
Staff Orthopaedic Surgeon, Mount Sinai Hospital, Toronto, ON

Introduction

Quadricep femoris (QF) muscle function is an integral factor in the rehabilitation and overall outcome after lower extremity injury or surgical intervention. Atrophy of this muscle group is a common finding in patients undergoing anterior cruciate ligament (ACL) reconstruction. This is due to the immobility prior to surgery, vascular ischemia caused by a tourniquet intra-operatively and inability to perform high load strength training in the early post-operative period¹. A deficit in QF muscle strength can result in excessive joint loading and be a contributing factor in the early onset of osteoarthritis of the knee². It should be noted that a loss of strength in this primary knee extensor mechanism muscle group can persist for up to 2 years after surgery³. Thus, the reduction of QF atrophy and maintenance of strength during an intervention such as an ACL reconstruction has large implications for the overall post-operative outcome and natural history of the knee joint.

In order to combat the challenges of muscle atrophy for patients with an ACL injury, blood flow restriction (BFR) training has been shown to have beneficial effects in the post-operative period specifically. The process of using BFR therapy involves the application of an extremity tourniquet to occlude venous outflow and restrict arterial inflow. Thus, an anaerobic environment is created to promote muscle hypertrophy by having cells upregulate cell signalling, protein synthesis and ultimately myogenic proliferation⁴. The use of BFR during lower extremity rehabilitation has shown that its simultaneous use with low load resistance training can have similar hypertrophic effects to isolated high load resistance training⁵. This is ideal for patients who are initially unable to perform high intensity exercises shortly after an ACL reconstruction surgery, but are attempting to reduce overall QF atrophy.

- Comorbidities including cardiovascular, respiratory or metabolic disease, blood coagulation disorders, current smoker

Outcome Variables:

- Primary: **Objective Quadricep (extension) and Hamstring (flexion) Strength**
 - Bidex Isokinetic testing
 - Measured in **Peak Torque (FT-LBS)**
 - Both flexion and extension measured at:
 - 60 degrees / second (indicative of **strength**)
 - 80 degrees / second (indicative of **endurance**)
 - Both the affected leg (ACL injury) and unaffected leg (CONTROL) were measured
- Secondary Outcomes:
 - Clinical Score
 - Organ Specific: (i.e. KOOS – Knee Injury and Osteoarthritis Outcome Score)
 - General Quality of Life: (i.e. SF-12 Score)
 - Clinical Exam: Thigh circumference (mm) – measured 10 cm superior to patella
- Independent Group Measures:
 - Patient Demographics: Age, Sex, Weight, Leg dominance, Injured leg side

BFR Cuff Details:

- 14 cm wide contoured pneumatic tourniquet cuff (Delfi VariFit Contour Thigh Cuff)
- Placed around proximal thigh, connected to portable pressure regulating system (Delfi Portable Tourniquet System)
- Inflated to 80% LOP (Limb Occlusion Pressure) – measured at initial visit via ultrasound probe or photoplethysmography probe

BFR Exercise Protocol: *To be completed at Mt. Sinai Hospital*

- Patient will perform a total of 12 sessions prior to surgery (3 sessions/week x 4 weeks)
- Patients will perform single leg knee extension exercise in a closed kinetic chain on a leg-press machine.
- Non injured leg will not perform any exercises but will act as control and be measured for strength and clinical outcome
- Patients in the non BFR group will perform the same protocol but there will be no inflation of their tourniquet during testing
- Load will be individually set to 15% 1RM for warm up and 25% 1RM for intervention
 - Warmup: 10 to 15 reps at 15% 1RM workload, no BFR occlusion
 - Rest: 30 seconds
 - 1st Set: cuff inflated to 80% LOP, patient completes 30 reps at 25% 1RM
 - Rest: 30 seconds
 - 2nd Set: cuff remains inflated to 80% LOP, patient completes 15 reps at 25% 1RM
 - Rest: 30 seconds
 - 3rd Set: cuff remains inflated to 80% LOP, patient completes 15 reps at 25% 1RM
 - Rest: 30 seconds
 - 4th Set: cuff remains inflated to 80% LOP, patient completes 15 reps at 25% 1RM
 - Session complete, cuff deflated.
- Load Progression
 - If patient's are able to complete all 75 repetitions (30-15-15-15) on two consecutive sessions, their load will be increased by 20 lbs at the subsequent session

Biodek Testing Protocol

- **Warm-up:** Stationary bike x 3-min
- **Biodek Set-up:** tall sitting with waist and thigh strap in place to secure limb, axis of movement through knee joint (1" above head of fibula)
- **Movement:**
 - Knee Extension (quadriceps kicking UP)
 - Knee Flexion (hamstrings pulling DOWN)
- **Muscle Activation:**
 - machine moves limb through a 70 degree range of movement while patient actively kicks up and down to get used to the pattern for the test
 - patient starts at 50% intensity x 5 reps and builds up slowly until they are ready to perform the test at 100% effort
- **Test:**
 - 5 repetitions @ **60** degrees/sec (heavy resistance) – **indicative of strength**
 - 10 repetitions @ **180** degrees/sec (lighter resistance) – **indicative of endurance**
- **Effort:** 100% for all 15 reps on both limbs
- **Results:** compared via print-out after the test and submitted for study

Intervention Timeline:

- Pre Op Period:
 - Phase One: Begins at time of initial consultation until 4 weeks pre operatively
 - This time allows for patient to reduce effusion, normalize range of motion prior to BFR intervention
 - Phase Two: Intervention period begins 4 weeks prior to surgery
 - 3 Sessions/week = 12 sessions total
 - Baseline Biodex testing completed at time = 0 weeks (4 weeks pre op)
 - This ensures patient is cleared for intervention to begin.
 - Pre-Operative Biodex testing completed at time = 4 weeks
 - This will be done prior to surgery once the physiotherapy protocol is completed.

Recruitment Strategy and Patient Screening:

All patients presenting to participating orthopaedic surgeons between the ages of 18 to 50 years with a diagnosis of an ACL injury requiring surgery will be screened. Potentially eligible patients will be approached by the site investigator to speak with a study coordinator to discuss participating in the trial. The study coordinator will be the one obtaining informed consent and no study related procedures will be done prior to subject signed the consent form.

Sample Size Estimation

Estimation of minimal sample size with a statistical power level of ≥ 0.80 (β -error $\leq 20\%$) was calculated based on the expected mean difference of our primary outcome measure (maximal voluntary isometric contraction, MVIC). The estimated minimal number of subjects for each treatment arm was 13 and 20% was added to account for loss to follow up. In total, 16 patients will be recruited to each pathway for a total of 32 individuals.

Budget

Item	Notes	Hours	Cost (per hour)	Cost
Delfi BFR Cuffs	Two sets of Delfi BFR Equipment	Nil	Nil	\$1600
Biodek Testing	1 on 1 strength assessments (30 min x 64 sessions)	32	\$120	\$3840
Physiotherapy	1 on 1 Physiotherapy (30 minute session x 384 sessions)	192	\$100	\$19,200
Data Collection and Analysis	Patient data collection and statistical analyses	200	Nil	Nil
			TOTAL	\$24,640

Study Facilities and Locations

- Each patient will complete twelve (12) physiotherapy sessions at the ***Rehab & Wellbeing Centre, Mount Sinai Hospital, [name]***
- Additionally, each patient will complete two (2) Biodek strength testing assessments at ***Cleveland Clinic Canada – Sport Medicine, [name]***

Research Team

- Principle Investigator: [name], MD
 - Resident Physician, Division of Orthopaedic Surgery, University of Toronto
- Primary Supervisor: [name], MD, FRCSC, MSc
 - Division of Orthopaedic Surgery, Mount Sinai Hospital, Toronto, ON
- Co-Supervisor: [name], MD, MBA
 - Clinical Fellow, University of Toronto Orthopaedic Sports Medicine
- Biodek Strength Testing Supervisor: [name], Athletic Therapist
 - Cleveland Clinic Canada – Sport Medicine Clinic, Toronto, ON
- Clinical Supervisor: [name], PA
 - Rehab & Wellbeing Centre, Mount Sinai Hospital, Toronto, ON

Significance

To date, the benefits of BFR for patients awaiting ACL surgery during the pre-operative period is extremely limited. This study will provide:

- The largest sample size to date for pre-operative BFR intervention in ACL patients
- High quality outcome testing in the form of Biodek isokinetic quadriceps strength testing
- An intervention protocol that involves the most BFR sessions per patient in the literature

If patients demonstrate favourable results prior to their surgery, this will provide some insight into the benefits BFR can have in patients awaiting ACL reconstruction.

References

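### Does tying the pre-operative Biodex test to completion of the physiotherapy protocol make measurement of the primary outcome depend on adherence?

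*Protocol*

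**What the plan says.** Under Intervention Timeline the protocol has two phases before surgery. For the second it says "Phase Two: Intervention period begins 4 weeks prior to surgery", at three sessions a week and 12 in total. Baseline strength is tested at week 0, with the note "This ensures patient is cleared for intervention to begin". For the second test it says "Pre-Operative Biodex testing completed at time = 4 weeks", followed by the note "This will be done prior to surgery once the physiotherapy protocol is completed".

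The BFR Exercise Protocol section gives the same 12 sessions over four weeks. It describes the comparator thus: "Patients in the non BFR group will perform the same protocol but there will be no inflation of their tourniquet during testing".

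Study Facilities and Locations states "Each patient will complete twelve (12) physiotherapy sessions" and, in a separate bullet, that each patient also has two strength assessments. The Budget lists 64 strength assessments and 384 physiotherapy sessions. On numbers, Sample Size Estimation says "The estimated minimal number of subjects for each treatment arm was 13 and 20% was added to account for loss to follow up", which gives 16 per arm and 32 in all.

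**The concern.** The second test is the only post-baseline measurement of the primary outcome, and its timing is described in two ways: by the calendar and by an event. The event, finishing the physiotherapy, happens after randomisation. If it governed, patients who stopped or fell behind might be tested late or not at all. One arm trains with an inflated cuff and the other without inflation, so completion could differ by arm. A comparison of completers alone would then lose the protection of randomisation.

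Surgery makes a missed pre-operative test unrecoverable, so an analysis plan could not repair the loss. Patients left untested would also use up the margin added to the sample size.

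**Working it through.** **1. The plan's own counts.**
- Sessions per patient: 3 per week x 4 weeks = 12.
- Physiotherapy sessions: 32 x 12 = 384, as budgeted.
- Strength tests: 32 x 2 = 64, as budgeted. This is one baseline and one later test for every recruited patient, with no deduction for non-completers.
- Patients per arm: 13 x 1.2 = 15.6, rounded up to 16, as stated. The base figure of 13 cannot be re-derived, because no effect size, SD or significance level is given.

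**2. Do the two timings conflict?** Programme length is 12/3 = 4.0 weeks. The end of the programme and week 4 coincide, so there is no contradiction on the planned schedule.

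**3. When would they separate?** Suppose k sessions are not made up in the same week and training continues at three per week. It then ends at (12 + k)/3 weeks: 4.33 weeks for k = 1 (0.33 x 7 = 2.3 days late) and 5.0 weeks for k = 3. But no section provides for training beyond week 4, and the sentence at issue requires the test before surgery, which is nominally at week 4. A test at 5.0 weeks is therefore excluded by the same sentence. A session moved within its week causes no delay, since weekdays are not fixed.

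**4. The sample-size margin.** 16 - 13 = 3, so an arm can lose three patients (3/16 = 18.75%) and keep 13. A full 20% loss leaves 16 x 0.80 = 12.8. That small shortfall comes from adding 20% to 13 rather than dividing by 0.80 (13/0.80 = 16.25, so 17). It has nothing to do with test timing.

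**5. What the harmful reading would cost, if it applied.** These figures rest on assumptions that are not in the protocol.
- Assume independent per-session attendance of 99%, 98% or 95% and no make-up sessions. The share finishing all 12 is 0.99^12 = 0.886, 0.98^12 = 0.785 or 0.95^12 = 0.540, which is 14.2, 12.6 or 8.6 of 16.
- Assume a two-sided 5% t-test and the standardised effect that gives 80% power at 13 per arm (1.15). Power is 0.88 at 16 per arm, 0.77 at 12 and 0.68 at 10.
- Assume no true effect, full completion among controls, completion c in the BFR arm, and correlation r between outcome and the tendency to complete. The bias is r x f(z)/c, where f is the standard normal density and z is the standard normal quantile at 1 - c. For r = 0.2 and c = 0.9 it is 0.2 x 0.1755/0.9 = 0.04 SD. For r = 0.6 and c = 0.7 it is 0.6 x 0.3477/0.7 = 0.30 SD.

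The figures in step 5 arise only if staff withhold the test from non-completers. The protocol does not tell them to.

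**The case for a change.** The best case for a change is this. The note under the baseline test has an operational role, since that test clears the patient to start; the matching note under the second test could be read the same way. Sessions and tests take place at different institutions, so someone must decide when to book, and two triggers are on offer. The schedule has no slack: a patient who falls behind and cannot catch up in the same week cannot be both finished and tested before surgery. The statement that each patient completes 12 sessions and two tests does not say what happens when only part of the first is done. A clarifying sentence would be cheap, and the tests are already paid for.

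Part of this stands. The two timings can separate once sessions are missed, no line says which governs, and a test missed before surgery is lost.

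The step from there to adherence-dependent measurement does not stand. It needs a reading that the protocol does not state and that its unconditional two tests per patient do not support. The note reads naturally as an order of events: training, then test, then surgery. Completing the protocol can equally mean reaching the end of the four-week programme.

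The sample-size argument is also weak. The figure of 13 was calculated for maximal isometric contraction, whereas the Biodex outcome is isokinetic peak torque, so falling to 12 establishes nothing about power for the latter. With a single follow-up test, an untested patient is a loss to follow-up, which is what the 20% was added for.

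**Conclusion.** No change to the plan follows. The two descriptions of the test's timing agree on the planned schedule, and testing of completers only is nowhere stated. The missing detail is what to do for a patient who misses or stops sessions. Staff can settle it from the text: the test belongs at week 4, it must precede surgery, and every patient is due two.

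This conclusion assumes that staff read the note as a sequence and do not cancel tests for incomplete attendance. If they did cancel them, the consequences could be material in a trial of 16 per arm. But the protocol has no attendance data from which to derive the number affected, and neither the direction nor the size of any bias can be established. If the sponsor chose to confirm to staff that the test does not depend on attendance, that would be a minor clarification of wording and not the correction of a design error.

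### The protocol specifies no masking of the Biodex tester, although the primary strength test depends on the patient's effort and is already run at a different clinic from the training

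*Protocol*

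**What the plan says.** - **Primary outcome.** Outcome Variables names "Objective Quadricep (extension) and Hamstring (flexion) Strength", measured as isokinetic peak torque.
- **How the value is produced.** Under Biodek Testing Protocol the effort required is "100% for all 15 reps on both limbs". Before the test the patient begins at half intensity and "builds up slowly until they are ready to perform the test at 100% effort". No number of further build-up steps, time limit or readiness criterion is given, and no script for instructions or encouragement.
- **When and where.** Study Facilities and Locations says that "each patient will complete two (2) Biodek strength testing assessments", at a sport medicine clinic. The twelve training sessions are at the hospital's rehabilitation centre. Intervention Timeline places the two tests at week 0 and week 4. Budget describes the tests as one-to-one, 30 minutes each. Research Team lists a testing supervisor, an athletic therapist, at "Cleveland Clinic Canada – Sport Medicine Clinic, Toronto, ON".
- **Comparator.** BFR Exercise Protocol gives controls the same exercises, but "there will be no inflation of their tourniquet during testing". Given the section it stands in, I read this as the training sessions. The uninflated cuff is not described as a sham or as a means of masking.
- **Secondary outcome.** "Thigh circumference (mm) – measured 10 cm superior to patella", with no assessor named.
- **Masking.** No section mentions masking of the tester, patient, physiotherapist or analyst.

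**The concern.** A dynamometer reads torque without judgement, but the torque depends on how hard the patient tries. A tester who knows the arm and expects BFR to work can, without intending to, coach some patients harder or let them build up for longer before the test. Any such difference between arms enters the primary comparison as if it were a treatment effect.

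Patients are unlikely to be unaware of their arm, so keeping the tester unaware is one of the few practical safeguards left. The separation of sites and staff makes it easy to arrange, yet the protocol does not use it. Masking is a matter of conduct: a statistical analysis plan cannot supply it once the tests have been done. The result also has a consequence, because the Introduction says that encouraging findings will lead to a fuller randomized trial.

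**Working it through.** **1. Is masking specified anywhere?** I read the whole protocol for it. It is absent from the design section, the outcome list, the testing protocol, the facilities section and the research team list.

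**2. Is there a route for bias?**

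| Condition | Where | Finding |
|---|---|---|
| Outcome depends on effort | Biodek Testing Protocol | Yes: full effort on every repetition |
| Discretion before the test | Biodek Testing Protocol | Yes: build-up has no stated end point |
| Close contact with a tester | Budget | Yes: one-to-one, 32 patients x 2 tests = 64 sessions |
| Patient can probably tell the arm | BFR Exercise Protocol | Yes: cuff at 80% of limb occlusion pressure versus no inflation |
| Allocation kept from the tester | No section | Not stated |

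The route is open as written. The protocol gives no information on whether it would operate, or how strongly.

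**3. The sample size, for the illustration.** Sample Size Estimation gives 13 per arm plus 20%: 13 x 1.2 = 15.6, rounded up to 16, which matches the plan. The concern does not rest on this figure. I use 13 per arm as the number completing.

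**4. Illustration with assumed shifts.** Assume a two-sample t-test at two-sided 5%, no true effect, and an additive shift of b standard deviations in favour of BFR.

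- Degrees of freedom: 2 x 13 - 2 = 24. Critical value: 2.064.
- Noncentrality: b x sqrt(13/2).
- Chance of a significant result favouring BFR: P(T > 2.064), with T noncentral t on 24 degrees of freedom.

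| b (assumed) | Noncentrality | Favouring BFR, 13 per arm | Either direction, 13 per arm | Favouring BFR, 16 per arm |
|---|---|---|---|---|
| 0 | 0 | 2.5% | 5.0% | 2.5% |
| 0.2 | 0.510 | 7.1% | 7.8% | 7.9% |
| 0.3 | 0.765 | 11.0% | 11.4% | 12.8% |
| 0.5 | 1.275 | 23.1% | 23.2% | 27.7% |

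The protocol anchors none of these shifts. The table shows how sensitive the comparison would be to a shift, not what shift to expect. Nor would all of such a shift need to come from the tester, since the patient's own expectation acts on the same measurement.

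**The case against.** The strongest reply is that this rests on silence. The protocol does not say that testers know the arm, and the sentence on two assessments per patient has nothing wrong in it. A reader might infer that testers are unmasked; the text supports only that masking is not specified. That limit stands. It does not remove the point, because the reader cannot look to the analysis plan for a conduct safeguard.

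Other stronger readings also go too far:

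- **That the tester steers the build-up, or accepts and rejects efforts.** The text describes the patient building up. It mentions no guidance, encouragement or acceptance rule. Coaching is a plausible channel in a one-to-one session, not a documented one. Set-up, warm-up and repetition counts are fixed.
- **That any bias could not be told apart from a true effect.** Each patient has a baseline test, and the untrained leg is measured at full effort too. General over-encouragement should partly show in that leg. Bias confined to the injured leg at week 4 would not, and the protocol does not define a between-leg contrast as the primary measure.
- **That tester masking is the only protection left, or is free.** Scripted instructions are a second protection. Withholding allocation needs a real procedure, because the testing supervisor is listed in the research team and patients can talk during a 30-minute session.
- **That patients cannot be masked.** An uninflated cuff makes it unlikely, but the protocol does not say what patients are told.
- **That thigh circumference suffers in the same way.** It is a measurement involving no maximal effort. The operator's placement and reading matter, which is a different mechanism in a secondary outcome.

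Finally, this is a feasibility study of 32 patients, so the standard might be thought lower. However, it randomizes, compares strength between arms, and is meant as a template for a larger trial.

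**Conclusion.** The concern holds in a limited form. The protocol specifies no masking of the tester for an effort-dependent primary outcome, in a trial where patients probably know their arm and where separate sites would make masking practicable. Nothing as written keeps the allocation from the tester, so an avoidable route to bias is open. The baseline test and the untrained leg would reveal such bias only in part.

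Its size is unknown. The range from 7.1% to 23.1%, against a nominal 2.5%, follows from assumed shifts of 0.2 to 0.5 SD with 13 per arm and is illustration only. A reader might take it as the trial's actual false-positive risk; the protocol gives no basis for that. No figure in the protocol changes. This should be corrected, but it is not fatal to the study.

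**What to change.** Add one paragraph to Biodek Testing Protocol stating that:

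1. the Biodex testers are not told the allocation;
2. test requisitions carry only a study number;
3. patients are asked before each test not to disclose their arm;
4. one scripted set of instructions and encouragement is used for every test, covering the build-up to full effort.

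Under Outcome Variables, state that thigh circumference is measured by someone who does not know the arm. If the Biodex tester does this, it takes a little time from a 30-minute session.

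The cost is the paragraph, an instruction to the testing clinic and a small procedural burden. No extra staff or visits are needed. Some patients may still disclose their arm, and patients' own expectation would remain, so the report should still name this as a limitation.
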